SMQ	Standard MedDRA Query

Abbreviation	Term
SOC	system organ class
SVR	spleen volume reduction
TEAE	treatment-emergent adverse event
[REDACTED]	[REDACTED]
[REDACTED]	[REDACTED]
T _{max}	time of occurrence of C _{max}
TSS	total symptom score
WBC	white blood cell
WHO	World Health Organization

1. INTRODUCTION

This is an open-label and sponsor-unblinded Phase 2 study with 2 cohorts.

- **Cohort A:** MF subjects who are tolerating a ruxolitinib dose of less than 20 mg daily with no dose increase or no dose modification in the 8 weeks before screening visit will receive a combination of the JAK1 inhibitor itacitinib at the dose of 200 mg QD and the JAK1/2 inhibitor ruxolitinib.
- **Cohort B:** MF subjects who, after an initial reduction in spleen with ruxolitinib treatment, progressed or discontinued for hematologic toxicities, will receive treatment with JAK1 inhibitor itacitinib alone at the dose of 600 mg QD.

Subjects will continue study treatment until disease progression, unacceptable toxicity, withdrawal of consent, or other Protocol-specified criteria to stop treatment are met. Subjects who are receiving benefit from the therapy will continue receiving study treatment until withdrawal criteria are met.

The protocol provides a detailed description of the investigational products, target patient population, rationale for doses to be examined, and potential risks and benefits of treatment with itacitinib.

The purpose of this SAP is to provide details of the statistical analyses that have been outlined in the Study INCB 39110-209 Protocol. The scope of this plan includes the interim and final analyses that are planned and will be executed by the Department of Biostatistics or designee. The analysis of PK [REDACTED] are not described in this SAP.

2. STUDY INFORMATION, OBJECTIVES, AND ENDPOINTS

2.1. Protocol and Case Report Form Version

This SAP is based on INCB 39110-209 Protocol Amendment 1 dated 14 AUG 2017 and CRFs approved 22 AUG 2017. Unless superseded by an amendment, this SAP will be effective for all subsequent Protocol amendments and CRF versions.

2.2. Study Objectives and Endpoints

Study objectives and endpoints are presented in [Table 1](#).

Table 1: Study Objectives and Endpoints

Primary Objective	Primary Endpoint
To evaluate preliminary efficacy of itacitinib on SVR from baseline at Week 24 in the 2 following cohorts of MF subjects: 
• Cohort A: in combination in subjects with ruxolitinib low dose (less than 20 mg daily).• Cohort B: as monotherapy in subjects who progressed (per revised ELN 2013 response criteria for MF) after initial reduction in spleen on ruxolitinib or discontinued for hematologic toxicities.	Change and percentage change in SVR as measured by MRI (CT scan in subjects who are not candidates for MRI or when MRI is not readily available) at Week 24 when compared with baseline.
Secondary Objectives (Cohorts A and B)	Secondary Endpoints
To evaluate preliminary safety and tolerability of itacitinib alone.	Safety and tolerability through assessment of frequency, severity, and duration of AEs; changes in clinical safety assessments; and changes in clinical laboratory parameters.
To evaluate preliminary safety and tolerability of itacitinib in combination with ruxolitinib.	Change and percentage change in SVR from baseline through Week 12 as measured by MRI (or CT scan in applicable subjects).
To evaluate preliminary efficacy of itacitinib alone or in combination with ruxolitinib on spleen length reduction from baseline at Week 12 and Week 24.	Change and percentage change in spleen length from baseline through Week 12 and Week 24 as measured by palpation.
To evaluate preliminary efficacy of itacitinib alone or in combination with ruxolitinib with respect to MF symptoms at Week 12 and Week 24.	Change and percentage change in TSS from baseline through Week 12 and Week 24 as measured by the MFSAF v2.0 symptom diary and by the MPN-SAF.
	PGIC score at each visit where the variable is measured.
To evaluate preliminary efficacy of itacitinib using IWG-MRT criteria.	Number of subjects with responses according to the 2013 IWG-MRT consensus criteria for treatment response.
To assess the PK of itacitinib and ruxolitinib.	Calculation of the PK parameters such as AUC, CL/F, C _{max} , and t _{max} along with summarization of the observed concentration data by timepoint will be performed for both ruxolitinib and itacitinib.

Table 1: Study Objectives and Endpoints (Continued)

3. STUDY DESIGN

This is an open-label Phase 2 study with 2 cohorts:

[figure not shown]
- **Cohort A:** MF subjects who are tolerating a ruxolitinib dose of less than 20 mg daily with no dose increase or no dose modification in the last 8 weeks before screening visit will receive a combination of the JAK1 inhibitor itacitinib at the dose of 200 mg QD and the JAK 1/2 inhibitor ruxolitinib.
 - **Cohort B:** MF subjects who, after an initial reduction in spleen with ruxolitinib treatment, progressed or discontinued for hematologic toxicities, will receive treatment with JAK1 inhibitor itacitinib alone at the dose of 600 mg QD.

Subjects will continue study treatment until disease progression, unacceptable toxicity, withdrawal of consent, or other Protocol-specified criteria to stop treatment are met. Subjects who are receiving benefit from the therapy will continue receiving study treatment until withdrawal criteria are met.

All subjects will be followed for safety 30 to 35 days after the last dose of study treatment (eg, reporting of AEs and SAEs).

The overall study design is shown in Figure 1.

Figure 1: Study Design

3.1. Randomization

Not applicable.

3.2. Control of Type I Error

The level of significance for detecting a difference from a 0% median percentage SVR in each cohort is 5% (1-sided). In other words, under the null hypothesis of subjects receiving itacitinib having a true median percentage SVR of 0%, there is a 5% chance of declaring a given cohort as having a median percentage $SVR > 0\%$. Note that this level of significance does not account for testing of multiple cohorts.

All other statistical analyses are exploratory in nature. Unless otherwise specified, all CIs provided will be at the 95% confidence level.

3.3. Sample Size Considerations

Up to 21 subjects will be enrolled in each of the 2 dose cohorts (Cohort A and Cohort B) for a total of 42 subjects overall. The sign test will be used to evaluate percentage change from baseline in spleen volume by MRI or CT at Week 24 in applicable subjects with a 1-sided Type I error of 0.05. If 15 or more out of 21 subjects observe a $> 0\%$ SVR at Week 24, then further development of itacitinib as monotherapy or in combination with ruxolitinib may be considered. If the percentage of SVR at Week 24 is normally distributed with mean 11.4 and standard deviation 14.5, the test has 85% power to indicate that additional development is warranted.

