7.3. Analysis of the Primary Efficacy Parameter

7.3.1. Primary Efficacy Analysis

The primary endpoint of change and percentage change of SVR (as measured by MRI or CT) at Week 24 will be summarized by cohort. Within each cohort, the sign test will be used to evaluate whether the median percentage of SVR is > 0%. For purposes of this test, subjects with missing Week 24 evaluations who discontinued prior to the planned Week 24 visit will be considered as not having achieved SVR. If 21 subjects are enrolled in a cohort, the null hypothesis of $\leq 0\%$ median SVR will be rejected if 15 or more out of 21 subjects observe a $> 0\%$ SVR at Week 24.

The baseline spleen volume will be assessed between Study Day -7 and Day 1 (inclusive) with the last value in the assessment window used if there are multiple values measured during this period. Subjects with missing baseline spleen volume will not be evaluable for this analysis. The Week 24 spleen volume will be assessed during Week 24 (Day 168 ± 7), and the last value in the assessment window will be used if there are multiple values measured during the Week 24 visit.

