11. INTERIM ANALYSES

Although no formal interim analysis for efficacy is planned, further enrollment in a cohort will be terminated if 7 or more subjects within the cohort fail to demonstrate SVR at Week 24 based on the primary endpoint of percentage change from baseline in spleen volume (by MRI/CT scan). Subjects will have failed to demonstrate SVR if they either 1) discontinue before the Week 24 assessment or 2) have an $SVR \leq 0$ at the Week 24 assessment.

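### The 85% power in SAP Section 3.3 leaves out the rule that counts discontinuation before Week 24 as failure, so it is a ceiling for the test as specified

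*SAP*

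**What the plan says.** Section 3.3 (Sample Size Considerations) sets the size of each cohort: "Up to 21 subjects will be enrolled in each of the 2 dose cohorts". It names a sign test on the Week 24 percentage change in spleen volume, at a 1-sided 5% level. Further development may be considered if 15 or more of 21 subjects show some reduction. The power statement follows: "If the percentage of SVR at Week 24 is normally distributed with mean 11.4 and standard deviation 14.5, the test has 85% power". The section mentions neither discontinuation nor missing scans.

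Section 7.3.1 (Primary Efficacy Analysis) specifies the same sign test and the same 15-of-21 cutoff, and adds a rule for missing data: "subjects with missing Week 24 evaluations who discontinued prior to the planned Week 24 visit will be considered as not having achieved SVR". Only subjects without a baseline spleen volume are taken out as non-evaluable.

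Section 11 (Interim Analyses) closes enrollment in a cohort at 7 or more failures and defines failure in a similar way: "Subjects will have failed to demonstrate SVR if they either 1) discontinue before the Week 24 assessment".

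Section 1 (Introduction) foresees that subjects may stop early: "Subjects will continue study treatment until disease progression, unacceptable toxicity, withdrawal of consent".

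**The concern.** Section 3.3 attaches the 85% to the test, and Section 7.3.1 defines that test. The power calculation uses only a normal distribution of Week 24 values. The test has a second route to failure, stopping without a Week 24 evaluation, and the calculation has no term for it. Nothing in the SAP says that the mean of 11.4 and the standard deviation of 14.5 already absorb such failures.

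The 85% supports the rule for considering further development. A reader would take the chance of missing the cutoff at the assumed effect to be 15%, when under Section 7.3.1 it is at least 15%. In a cohort of 21, missing the cutoff means 7 or more failures (21 − 14 = 7), which is also the count at which Section 11 ends enrollment.

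**Working it through.** **Inputs from the SAP.** n = 21 per cohort; success is a reduction above 0% at Week 24; cutoff 15 of 21; mean 11.4 and SD 14.5 (all Section 3.3). Discontinuation without a Week 24 evaluation counts as failure (Section 7.3.1). The discontinuation rate is not given, so the rates below are assumptions.

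**Step 1: reproduce the stated figure.**
- p = Φ(11.4/14.5) = Φ(0.786) = 0.7841
- Power = P(Bin(21, 0.7841) ≥ 15) = 0.8516

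This matches 85% and requires a Week 24 value from all 21 subjects.

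**Step 2: lose k subjects at random, each scored as a failure.** The other 21 − k must still supply 15 successes: P(Bin(21 − k, 0.7841) ≥ 15).
- k = 1: 0.7494
- k = 2: 0.6074

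**Step 3: apply an assumed discontinuation rate.** Let d be the share of subjects who discontinue without a Week 24 scan, and f the share of those who would have failed anyway. Only lost would-be responders matter:

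Power = P(Bin(21, p − d(1 − f)) ≥ 15)

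If discontinuation is independent of response, f = 1 − p = 0.2159 and the success probability is p(1 − d). For example, at d = 0.10 it is 0.7841 × 0.90 = 0.7057, and power is 0.5735.

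| Share who would have failed anyway (f) | d = 5% | d = 10% | d = 20% |
|---|---|---|---|
| 0.2159 (independent of response) | 72.5% | 57.4% | 28.0% |
| 0.50 | 77.5% | 68.5% | 48.7% |
| 0.75 | 81.5% | 77.5% | 68.5% |
| 1 (all) | 85.2% | 85.2% | 85.2% |

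No cell exceeds 85.2%.

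**Step 4: find where power reaches 80%.** This happens at a success probability of 0.7667, that is, when lost would-be responders make up 0.7841 − 0.7667 = 0.0174 of all subjects. Dividing by 1 − f gives a discontinuation rate of 2.2% (independent), 3.5% (f = 0.5) or 7.0% (f = 0.75).

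**Step 5: check the type I error.** P(Bin(21, 0.5) ≥ 15) = 0.0392. With independent discontinuation of 5%, 10% and 20% it is 0.0233, 0.0132 and 0.0036. The failure rule makes the test more conservative.

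**The case against.** **The statement is conditional and true.** Section 3.3 begins with an assumption about the distribution, and the arithmetic under it is right. That stands: nothing was miscalculated. But the condition covers only the distribution of Week 24 values, while the conclusion is about a test that also fails subjects who have no value.

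**The wording about applicable subjects may limit the calculation to those scanned.** The phrase is "in applicable subjects with a 1-sided Type I error of 0.05". The cutoff nevertheless stays at 15 of 21 in both sections, and Section 7.3.1 keeps those who discontinue in the test as failures.

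**The protocol, not shown here, may give the source of 11.4 and 14.5 or an expected discontinuation rate.** It may. The SAP still states its own power figure and attaches it to its own test without saying how the failure rule was treated. A normal distribution of percentage reduction also has no component for subjects without a measurement.

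**The table depends on what the normal distribution describes.** This is the strongest point. The rows with f = 0.5, 0.75 and 1 treat it as the potential outcome of every subject, scanned or not. If it describes only subjects with a Week 24 value, the success probability is p(1 − d) whatever the others would have done, and only the 73%, 57% and 28% row applies. On that reading, losing a subject who would have failed anyway is not free. The direction is the same under both readings, and the less favourable figures already lie within the range shown.

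**The consequence is limited.** The decision rule is permissive, the study is an exploratory Phase 2 trial, and the failure rule is conservative. The Section 11 stop costs no further power at n = 21, because 7 failures already rule out 15 successes. All of this is fair, and it is why the remedy is confined to wording.

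**Conclusion.** The concern holds. The 85% is correct for complete Week 24 data and an upper bound for the test in Section 7.3.1. The direction needs no assumption about rates, because scoring a discontinued subject as a failure can never add a success.

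The size does rest on assumptions. If the normal model covers all subjects, 85% is reached only when no would-be responder is lost without a scan, and power is below 80% once such losses exceed 1.7% of subjects. At assumed discontinuation rates of 5% to 20%, power runs from 85% (all of those lost would have failed) down to 28% (20% lost independently of response). Disease progression is a listed reason for stopping, so full independence may be the pessimistic end. If the model covers only subjects with a Week 24 value, the independent row applies. The risk is a missed active regimen, since the type I error stays at or below 3.9%. This should be fixed.

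**What to change.** Reword the power sentence in Section 3.3 to say that, under the stated normal distribution, power is at most 85%, and that this makes no allowance for would-be responders who discontinue without a Week 24 evaluation and are scored as failures under Section 7.3.1.

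Then give power at the sponsor's expected discontinuation rate. If there is no expected rate, give the range and label it as assumed. At 5%, 10% and 20% discontinuation:
- independent of response: 73%, 57% and 28%
- half would have failed anyway: 78%, 69% and 49%
- three quarters would have failed anyway: 82%, 78% and 69%
- all would have failed anyway: 85% at each rate

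State also whether the normal distribution is meant for all subjects or only for those with a Week 24 value, because the last three rows need the former.

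The cost is SAP wording and a less favourable power statement. The test, the cutoff and the sample size do not change.

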3.4. Schedule of Assessments

Refer to Protocol Amendment 1 dated 14 AUG 2017 for a full description of all study procedures and assessment schedules for this study.

4. DATA HANDLING DEFINITIONS AND CONVENTIONS

4.1. Scheduled Study Evaluations and Study Periods

4.1.1. Day 1

Day 1 is the date that the first dose of itacitinib is administered to the subjects.

4.1.2. Study Day

If a visit/reporting date is on or after Day 1, then the study day at the visit/reporting date will be calculated as

$$\text{Day \#} = (\text{Visit/Reporting Date} - \text{Day 1 date} + 1).$$

If the visit/reporting date is before Day 1, then the study day at the visit/reporting date will be calculated as

$$\text{Day \#} = (\text{Visit/Reporting Date} - \text{Day 1 date}).$$

A study day of -1 indicates 1 day before Day 1.

4.1.3. Baseline Value

Baseline is the last nonmissing measurement obtained before the first administration of itacitinib, unless otherwise defined.

When scheduled assessments and unscheduled assessments occur on the same day and time of the assessment or time of first dose is not available, use the following convention to determine baseline:

- If both a scheduled and an unscheduled visit are available on the day of the first dose and the time is missing, use the scheduled assessment as baseline.
- If all scheduled assessments are missing on the day of the first dose and an unscheduled assessment is available, use the unscheduled assessment as baseline.

4.1.4. Handling of Missing and Incomplete Data

In general, values for missing data will not be imputed unless methods for handling missing data are specified in this section or relevant sections.

Partial MF diagnosis date will be handled as follows:

- If only the day is missing, then the imputed day will be the first of the month.
- If both the month and day are missing, then the imputed day and month will be 01 JAN.

- No imputation will be done if the date is completely missing.

Missing or partial date of last dose will be handled as follows:

- If only the day is missing, then the imputed date of the last dose will be the earlier date of the first day of the month or the date that the subject discontinued treatment.
- Otherwise, the date that the subject discontinued treatment will be used as the date of the last dose.

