5. STATISTICAL METHODOLOGY

5.1. General Methodology

Unless otherwise noted, SAS® software (SAS Institute Inc, Cary, NC; Version 9 or later) will be used for the generation of all tables, graphs, and statistical analyses. Descriptive summaries for continuous variables will include, but not be limited to, the number of observations, mean, standard deviation, median, minimum, and maximum. Descriptive summaries for categorical variables will include the number and percentage of subjects in each category.

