6.4. Exposure

For subjects in the safety population, exposure to itacitinib and ruxolitinib will be summarized descriptively as the following:

- **Duration of treatment with itacitinib (days):** date of last dose of itacitinib – date of first dose of itacitinib + 1. For subjects who are continuing to receive itacitinib at the time of the analysis, the date of the last visit will be used.
Average daily dose of itacitinib (mg/day): total actual itacitinib dose taken (mg) / duration of treatment with itacitinib (days). Total actual dose of itacitinib will be calculated based on the information entered on the drug accountability CRF.
- **Itacitinib dose modifications:** Number of subjects who had itacitinib dose reductions or interruptions will be summarized.
- **Duration of treatment with ruxolitinib (days):** date of last dose of ruxolitinib – date of first dose of on-study ruxolitinib + 1. For subjects who are continuing to receive ruxolitinib at the time of the analysis, the date of the last visit will be used.
- **Average daily dose of ruxolitinib (mg/day):** total actual on-study ruxolitinib dose taken (mg) / duration of treatment with ruxolitinib (days).
- **Ruxolitinib dose modifications:** Number of subjects who had ruxolitinib dose reductions or interruptions on-study will be summarized.

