6.5. Study Drug Compliance

For subjects in the safety population, overall compliance (%) for itacitinib will be calculated for all subjects as

$$\text{compliance (\%)} = 100 \times [\text{total dose actually taken}] / [\text{total prescribed dose}].$$

The total prescribed dose is defined as the sum of the doses prescribed by the investigator accounting for dose modifications.

The total actual dose taken will be calculated based on information entered on the drug accountability CRF. If there is dispensed drug that has not been returned yet, the actual dose taken starting from the dispense date of the unreturned drug will be imputed by the dose taken as reported on the dosing CRF.

Compliance for ruxolitinib will not be calculated.

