10.3.2. Laboratory Value Summaries

All test results and associated normal ranges from central laboratories will be reported in SI units. All tests with numeric values will have a unique unit per test. Any laboratory test results and associated normal ranges from local laboratories will be converted to SI units. For the limited number of cases where the associated normal ranges from a local laboratory cannot be obtained despite due diligence, a set of standard normal ranges based on documented reference ranges will be applied to facilitate reporting the test results.

When there are multiple laboratory nonmissing values for a subject's particular test within a visit window, the convention described in [Table 3](#) will be used to determine the record used for by-visit tabulations and summaries.

Table 3: Identification of Records for Postbaseline By-Visit Summaries

Priority	Laboratory Visit	Proximity to Visit Window	Tiebreaker
1	Scheduled	In-window	Use smallest laboratory sequence number
2	Unscheduled	In-window	
3	Scheduled	Out-of-window	

Numeric laboratory values will be summarized descriptively in SI units, and non-numeric test values will be tabulated when necessary. In addition, line graphs and box-and-whisker plots will be provided for hemoglobin, platelet counts, WBC, and neutrophils.

Shift tables based on worst postbaseline value recorded will use all postbaseline values occurring within 30 days of stopping study treatment. Shift summaries will be produced for each test for the safety population. The denominator for the percentage calculation will use the number of subjects in the baseline category (ie, low, high, normal, missing) as the denominator for the percentage in each of the categories during the treatment period.

Shift tables will be presented showing change in CTCAE grade from baseline to worst grade postbaseline. Separate summaries for abnormally high and abnormally low laboratory values will be provided when the laboratory parameter has both high and low grading criteria. The denominator for the percentage calculation will be the number of subjects in the baseline category.

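### The rule for a last-dose date with a missing day has no floor at first dose, so a same-month start and stop can give a zero or negative exposure duration

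*SAP*

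**What the plan says.** SAP Section 4.1.4 has two rules for an incomplete last-dose date. If only the day is missing, "the imputed date of the last dose will be the earlier date of the first day of the month", with the date of treatment discontinuation as the alternative. For every other case, "Otherwise, the date that the subject discontinued treatment will be used as the date of the last dose".

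Section 6.4 defines itacitinib duration as "date of last dose of itacitinib – date of first dose of itacitinib + 1" and ruxolitinib duration as "date of last dose of ruxolitinib – date of first dose of on-study ruxolitinib + 1". For each drug the average daily dose is the total dose taken divided by that duration. Subjects still on treatment at the time of analysis are given the last visit date instead. Section 5.1 has continuous variables summarised by "the number of observations, mean, standard deviation, median, minimum, and maximum", among others.

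The SAP nowhere requires the imputed last dose to be on or after the first dose.

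**The concern.** The rule takes the earlier of two dates. Treatment discontinuation normally falls on or after the last dose, so the first of the month is nearly always chosen, and the discontinuation date almost never acts as a cap. The first of the month is the earliest day that the known month allows. If the subject also started treatment in that month, on the 2nd or later, the imputed last dose comes before the first dose.

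At stake is an impossible value in the itacitinib or ruxolitinib exposure tables. It would appear as the minimum and would enter the mean. Cohorts hold up to 21 subjects (Section 3.3), so one such value is not diluted much. A programmer who noticed it would have to depart from the SAP with no rule to follow.

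**Working it through.** The SAP states no figure on this point to reproduce. The check puts the Section 4.1.4 rule into the Section 6.4 formula.

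**Same-month start and stop.** First dose on day d, discontinuation in the same month or later, so the imputed last dose is day 1.

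Duration = 1 - d + 1 = 2 - d

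| First dose on day | Duration under the rule | With a floor at first dose |
|---|---|---|
| 1 | 1 | 1 |
| 2 | 0 | 1 |
| 3 | -1 | 1 |
| 10 | -8 | 1 |
| 20 | -18 | 1 |
| 31 | -29 | 1 |

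Only a first dose on the 1st escapes.

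**The two rules side by side (assumed dates).** First dose 10 March, last dose and discontinuation 23 March. True duration is 23 - 10 + 1 = 14 days.
- Month known, day missing: 1 - 10 + 1 = -8 days.
- Date wholly missing: the discontinuation date is used, giving 14 days.

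Knowing the month gives the worse answer here. That ordering depends on how promptly discontinuation is recorded. With discontinuation recorded on 5 April, the second rule gives 27 days instead of 14.

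**Average daily dose, same subject at 600 mg/day.** Total taken is 14 × 600 = 8400 mg. If that total stays whole, the average is 8400 / (-8) = -1050 mg/day. With one such subject and 20 others at exactly 600 mg/day (assumption), the mean of 21 moves by (600 + 1050) / 21 = 79 mg/day. For a first dose on the 2nd the divisor is 0 and the average is undefined.

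**Last dose in a later month than first dose.** A true last dose on day k is moved back by k - 1 days, so 0 to 30 days are lost. If stop days are uniform (assumption), the mean loss is 13.5, 14.5 or 15 days in months of 28, 30 or 31 days. The effect of a 15-day loss on the average dose at 600 mg/day depends on the dose total:
- Total stays whole: 600 × 84 / 69 = 730 (+22%) for 84 true days, and 600 × 168 / 153 = 659 (+10%) for 168.
- Total cut at the same imputed date: 600 × 69 / 69 = 600, no error.

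The SAP does not settle which applies. Section 6.4 says "Total actual dose of itacitinib will be calculated based on the information entered on the drug accountability CRF", but Section 6.5 adds that, for dispensed drug not yet returned, the dose taken "will be imputed by the dose taken as reported on the dosing CRF".

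**The case against.** The strongest reply is that only the missing floor is an error. Setting a day-missing last dose to the first of the month is a definite rule, and it never overstates exposure when the recorded month is right. This stands. A reader might infer that the default itself is wrong and must move to the end of the month. The SAP does not support that: month end reverses the direction of the bias, its largest error in days is the same, and which default lies closer depends on a recording lag that the SAP does not give.

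A reader might also infer that the 30-day window for the laboratory shift tables closes early. Section 10.3.2 says that those tables "will use all postbaseline values occurring within 30 days of stopping study treatment". Section 4.1.4 treats the last dose and the discontinuation of treatment as separate dates, and the phrase fits the second at least as well. That date is not imputed. An effect follows only if the window is tied to the imputed last dose, which the SAP does not say.

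The case is also rare. It needs a first dose on the 2nd or later, a last dose in the same calendar month, and a known month with an unknown day. With at most 42 subjects it may never occur. A negative minimum would also be visible in the table rather than hidden. Both remarks bear on severity. Neither answers why a rule written for this very case should return an impossible value.

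**Conclusion.** The rule as written gives a duration of 2 - d days when first and last dose share a month, which is zero or negative for any d of 2 or more. This follows from Sections 4.1.4 and 6.4 alone and needs no assumption about the data beyond the case arising. The average daily dose is then undefined or, where the dose total is positive, negative.

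The loss of 0 to 30 days in other months is a property of the convention, not a separate error. The percentages for average dose and the shift of 79 mg/day in a cohort mean are illustrations that rest on a whole dose total and assumed dates. They are not estimates of what will happen.

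Severity is minor. Exposure duration is not an endpoint in Table 1, the adverse event summaries in Section 10.2.3 are counts and percentages of subjects, and the primary sign test in Section 7.3.1 does not use the last-dose date.

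**What to change.** Add to the day-missing rule in Section 4.1.4: *but not before the date of first dose of that drug*, and apply it to itacitinib and to on-study ruxolitinib. This costs one clause and one line of code, with no data cost.

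The floor makes the duration possible, not accurate. In the March example it gives 1 day instead of 14, and a whole dose total would then give 8400 / 1 = 8400 mg/day. The sponsor should therefore also say how the average daily dose is shown when the floor applies, for example left missing with a footnote.

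Optionally, the default could become the earlier of the last day of the month and the discontinuation date, with the same floor. In the March example this gives the true 14 days. Its cost is the opposite bias:
- Discontinuation recorded 2 days late gives 16 days, and 8400 / 16 = 525 mg/day.
- Discontinuation recorded in April gives 22 days, and 8400 / 22 = 382 mg/day (-36%).
- At worst, 84 true days ending on the 1st of a 31-day month become 114 days, and 600 × 84 / 114 = 442 mg/day (-26%). Under the present rule the largest loss is also 30 days.

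The existing rule for other incomplete dates already accepts this kind of lag, so the choice is the sponsor's.
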